7.2 Statistical Methods

The full analysis dataset will be based on a modified intent-to-treat principle. Randomized subjects receiving blinded study drug will be included and analyzed based on their randomized assignment. Patients meeting exclusion criteria or withdrawing after initial screening and randomization are excluded from all analyses. Safety outcomes will analyze patients based on treatment received. Evaluable analysis sets will be defined and will include data from subjects who have the necessary baseline and on study measurements to provide interpretable results for specific parameters of interest.

Descriptive Statistics

Data will be described and summarized by study drug assignment (entolimod 1 μ g, 3 μ g, 10 μ g, or placebo) and time point. Descriptive summaries will include sample size, mean and standard deviation, median, 25th and 75th percentiles, minimum and maximum for continuous variables and percentage for categorical variables. Baseline/screening data will be summarized by randomized group using median (25th-75th) percentiles and percentage for continuous and categorical data, respectively. Study drug administration, concomitant medication use, supportive care use, AEs, laboratory abnormalities, vital signs/oxygen saturation, body weight, virology data, quality of life and frailty index status will be described and summarized.

Primary Hypothesis: We hypothesize that entolimod will cause an increase in influenza antibody titers at 4 weeks in comparison to placebo

The distribution of antibody titers (A/H1N1, A/H3N2, B) during follow up is anticipated to be skewed based on reporting in prior studies and a log-transformation will be applied to these outcomes. Antibody titers are measured at multiple time points in the first week after treatment, 4 weeks, 2 months, 6 months, and 12 months. A hierarchical mixed-effects regression model will be fit separately for the 3 endpoints, adjusting for the baseline/screening observation of the titer (an analysis of covariance (ANCOVA) approach). The model will include random subject-specific intercepts and model time as discrete. The primary outcome comparison is a contrast analysis of the outcome at 4 weeks comparing each entolimod dose to placebo. As the overall aim of this study is to assess safety and identify potential efficacy of entolimod, especially the dose most likely to succeed in Phase III study, we apply a one-sided test at alpha level 0.15 to each dose comparison (vs. placebo) and antibody titer combination, without multiplicity adjustment. The primary analysis will be conducted using the modified intent-to-treat analysis dataset.

Secondary Hypotheses: Secondary and exploratory endpoints require a variety of standard statistical methods.

Key secondary endpoints include the frailty indices, measures of physical function (6 minute walk test and grip strength), and quality of life (QOL). Frailty indices are measured at 2, 6, and 12 months and QOL measured at each study visit. For these outcomes, linear mixed effects models will assess the relationship between randomized arm and outcomes over time. Discrete times will be considered corresponding to the study visit and secondary analyses may consider continuous linear time (constant slope over time) for changes in the outcome. For these outcomes, the 12 month observation is the primary comparison.

Upper respiratory infections, including influenza, will be recorded over the follow up period. We anticipate the total number of these will be infrequent. Thus, we compare the outcome of any infection (vs. no infection) across randomized arms using a Pearson chi-square test or Fisher's exact test. Secondary approaches may consider analysis of the ordinal count of the number of infections, analyzed using a trend test.

Cellular immune response and pharmacodynamics parameters, including concentration of circulating plasma cytokines and cytokine response to viral stimulation are outcomes compared using analysis of variance (ANOVA) methods across the four comparison groups. Pharmacodynamic measures will be listed and will be summarized using appropriate graphical and tabular methods. Statistical analysis evaluating pharmacodynamic parameters will be performed using contrasts in the context of analysis of covariance (ANCOVA).

Handling of Missing Data

In the analysis of primary outcomes, data are analyzed using a hierarchical regression approach assuming missing data are missing at random. In a secondary approach, patients with dropout or missing follow up due to influenza viral infection during follow up will be assumed missing not at random and missing data will be imputed to the baseline/screening value reflecting no increase

from baseline in antibody titers among these patients. Dropout for other causes will be considered similarly, except death unrelated to influenza, which will continue to be assumed as missing at random.

Interim Analysis

No interim analysis will be performed for efficacy assessment.

Multiplicity

No adjustments will be made for multiplicity correction to dose comparisons or the primary endpoints as the study aim is to identify promising doses for subsequent phase III study. Secondary outcomes will also not be adjusted for multiple comparisons.

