4.4 Early Withdrawal of Subjects

4.4.1 When and How to Withdraw Subjects

The following conditions describe the circumstances under which a subject may be withdrawn from the study prior to that subject completing all of the study related procedures:

- Any SAE that precludes further participation of the subject;
- With respect to subjects that have not received study drug, any SAE related to the study drug that in the opinion of the principle investigator or monitors as part of the Data and Safety Monitoring Plan (DSMP) which places subjects at high risk of experiencing the same SAE.
- If in the opinion of the principle investigator, there is doubt that a subject, for any reason, can continue to fully participate in the study; and
- Subject decision to withdraw from the study (withdrawal of consent).

See also Section 10.1, “Study Monitoring Plan”.

In the event of a subject withdrawal, the following will be performed:

- Review of data collected through the last in-person or remote visit for completeness;
- Replacement of study subject if the subject did not receive study drug (i.e., early withdrawal before study drug administration); and
- Follow-up for subjects withdrawn from study, if the treatment visit was completed. The exit visit will include those study assessments and procedures that would have been performed at the next scheduled visit.

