4.4.2 Data Collection and Follow-up for Withdrawn Subjects

If a subject withdraws consent to participate in the study, for subject safety or other reasons, attempts will be made to obtain permission to collect follow up information whenever possible, including through medical chart review. As outlined in section 4.4.1, “When and How to Withdraw Subjects,” the exit visit will include those study assessments and procedures that would have been performed at the next scheduled visit. Although early withdrawal could be related to the safety profile of the study drug, it could also be related to other reasons, and thus follow-up assessments could be important in capturing both additional safety information as well as study outcomes that affect interpretation of risk versus benefit. Since the study drug will be given only once, long-term safety consequences related to participation are expected to be very limited.

5 Study Drug

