For this study, the study treatment follow-up period is defined as (365) days following the last administration of study treatment.

Preexisting Condition

A preexisting condition is one that is present at the start of the study. A preexisting condition should be recorded as an adverse event if the frequency, intensity, or the character of the condition worsens during the study period.

General Physical Examination Findings

At screening, any clinically significant abnormality should be recorded as a preexisting condition. At the end of the study, any new clinically significant findings/abnormalities that meet the definition of an adverse event must also be recorded and documented as an adverse event.

Post-study Adverse Event

All unresolved adverse events should be followed by the sponsor-investigator until the events are resolved, the subject is lost to follow-up, or the adverse event is otherwise explained. At the last scheduled visit, the sponsor-investigator should instruct each subject to report, to the sponsor-investigator, any subsequent event(s) that the subject, or the subject's personal physician, believes might reasonably be related to participation in this study.

Abnormal Laboratory Values

A clinical laboratory abnormality should be documented as an adverse event if it changes from value within the normal range before treatment to one outside and worse than the normal range after treatment. Such changes will prompt a repeat test, telephone call to check the subject's status, a repeat visit, and/or referral to the subject's primary care physician.

Hospitalization, Prolonged Hospitalization or Surgery

Any adverse event that results in hospitalization or prolonged hospitalization should be documented and reported as a serious adverse event unless specifically instructed otherwise in this protocol. Any condition responsible for surgery should be documented as an adverse event if the condition meets the criteria for an adverse event.

Neither the condition, hospitalization, prolonged hospitalization, nor surgery are reported as an adverse event in the following circumstances:

- Hospitalization or prolonged hospitalization for diagnostic or elective surgical procedures for a preexisting condition. Surgery will **not** be reported as an outcome of an adverse event if the purpose of the surgery was elective or diagnostic and the outcome was uneventful.

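### Section 7.2 as written removes anyone who withdraws after randomisation, dosed or not, from every analysis, including safety

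*Combined protocol and SAP*

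**What the plan says.** The opening paragraph of section 7.2 defines a modified intent-to-treat set: "Randomized subjects receiving blinded study drug will be included and analyzed based on their randomized assignment". The next sentence reads: "Patients meeting exclusion criteria or withdrawing after initial screening and randomization are excluded from all analyses". The sentence after that says safety is grouped by treatment received. Section 7.3 only points back to these methods.

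Three other parts of the plan bear on the same subjects:

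- **Section 4.4.1** lists the reasons for withdrawal, beginning with "Any SAE that precludes further participation of the subject". It provides an exit visit for subjects who withdraw after the treatment visit. It limits replacement, but not exclusion from analysis, to undosed subjects: "Replacement of study subject if the subject did not receive study drug (i.e., early withdrawal before study drug administration".
- **Section 4.4.2** gives the reason for following withdrawn subjects: "follow-up assessments could be important in capturing both additional safety information as well as study outcomes that affect interpretation of risk versus benefit".
- **Section 7.2, Handling of Missing Data**, analyses the primary outcomes with a mixed model under missing at random. A secondary approach imputes the baseline value for influenza-related dropout, and then: "Dropout for other causes will be considered similarly, except death unrelated to influenza, which will continue to be assumed as missing at random".

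**The concern.** The exclusion sentence fixes only one time point, randomisation. It does not mention dosing, and its scope is every analysis. A subject who is injected, has an SAE and withdraws therefore meets the rule for inclusion and, one sentence later, the rule for exclusion.

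Section 3.4 names two primary endpoints, immunogenicity and safety, and both are exposed. Withdrawal after dosing is a post-randomisation event that treatment may influence. Removing those who withdraw means the week-4 titre contrast no longer compares the groups as randomised and dosed. On the safety side, subjects who leave because of harm would be missing from the final tables, in a dose-escalation study of people aged 65 or older. With 25 subjects planned per arm, each one deleted is 1/25 = 4% of that arm.

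There is also a plain reproducibility problem. Two statisticians working from the same paragraph could build different primary datasets, and each could cite the text in support.

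**Working it through.** **The texts side by side.** Take a subject who is randomised, dosed, has the 4-week titre drawn, and withdraws in month 5.

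1. Inclusion sentence (7.2): in the set, analysed as randomised.
2. Exclusion sentence (7.2): out of all analyses.
3. Safety sentence (7.2): says which arm a subject is counted in. It does not bring back anyone already excluded.
4. Missing-data text (7.2): the observed titres stay in the mixed model. In the secondary approach the missing later titres are imputed. If withdrawn subjects are deleted first, this plan has little left to act on beyond visits missed without withdrawal.
5. Sections 4.4.1 and 4.4.2: an exit visit is done because the data matter for safety and for weighing risk against benefit. Deletion would leave those data unanalysed.
6. Section 7.3: refers back and resolves nothing.

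Only item 2 removes the subject.

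**Does a pre-dose reading rescue the sentence?** On that reading, undosed subjects are already outside the set by the inclusion sentence, so the withdrawal clause adds nothing. Section 4.4.1 also shows that the authors state the pre-dose limit where they intend it. Both points count against assuming the limit here, though neither proves what was meant.

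**How many observed primary titres are exposed?** The plan gives no figure to reproduce and no withdrawal rate, so neither the number of subjects lost nor the bias can be computed. The timing can.

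- Time of the primary outcome: "The primary outcome comparison is a contrast analysis of the outcome at 4 weeks comparing each entolimod dose to placebo", taken as day 28.
- Length of follow-up: "the study treatment follow-up period is defined as (365) days following the last administration of study treatment".
- Visit window for Month 1 (Table S-1): ± 1 week, so day 35 at the late edge.

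Share of follow-up after the primary titre = (365 − t) / 365:

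- t = 28: (365 − 28) / 365 = 337 / 365 = 92.3%
- t = 35: (365 − 35) / 365 = 330 / 365 = 90.4%

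Let p be the fraction of withdrawals that occur before the titre is drawn. The share of withdrawn subjects whose observed primary titre would be deleted is then 1 − p, assuming the sample was taken:

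- Withdrawals spread evenly (assumption): p = 28 / 365 = 7.7%, share 92.3%, about 9 in 10.
- Half before day 28 (assumption): p = 50%, share 50%, or 5 in 10.
- All before day 28 (limiting case): p = 100%, share 0.

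These are shares of withdrawn subjects, not of the trial, and they do not estimate bias.

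**The case against.** The strongest reply is that the context shows a harmless intention. The paragraph announces a modified intent-to-treat set, ties it to dosing, and then names who falls out. The exclusion could refer to the short interval at Visit 2 between randomisation and injection, when pre-dose checks are made. The replacement rule, the exit visit and the detailed dropout plan all fit that reading. Protocols also often state an inclusion rule and then repeat its converse, so redundancy is weak evidence of a different intention. On this view the harm arises only if someone applies one sentence against its neighbours.

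Much of this is fair. The benign reading is plausible, and it may be what the authors meant. It is not what the sentence says, however, and an analysis-set definition has to work as written. The passages that suggest the intention are the same ones that the literal text contradicts.

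Two further points stand in part:

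- The 9-in-10 figure depends on an even spread of withdrawals that nothing in the documents supports. It describes exposure only, and the case does not rest on it.
- Safety oversight during the trial is not affected, because section 8.5.1 gives the DSMB all adverse event reports, unblinded. The exposure is in the final analyses.

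It can also be said that keeping dosed but ineligible subjects goes beyond a point about withdrawal. But the same sentence excludes them, and keeping them follows from the plan's own rule that randomised, dosed subjects are included.

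Withdrawal of authorisation does not require deletion either: section 9.1 lets the investigator use information collected before the revocation.

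**Conclusion.** The concern holds and must be fixed. As written, section 7.2 excludes dosed subjects who withdraw from all efficacy and safety analyses. That conflicts with the inclusion sentence immediately before it, with the missing-data plan and with the stated purpose of following withdrawn subjects. This conclusion rests on the wording alone and needs no assumption.

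The size of any bias is unknown, since no withdrawal rate is stated. Between 90% and 92% of follow-up lies after the primary titre. The share of withdrawn subjects who would have an observed titre deleted is about 9 in 10 under even withdrawal, 5 in 10 if half withdraw before day 28, and 0 if all do. Confidence is high that the text is contradictory; whether data would in fact be deleted depends on how the analyst reads it.

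**What to change.** Replace the exclusion sentence in section 7.2 with wording such as:

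> *Only randomised subjects who never received study drug are excluded. All randomised and dosed subjects are analysed: efficacy by randomised arm, using all available titres, and safety by treatment received. Withdrawal, or an eligibility deviation identified after dosing, does not remove a subject from either set.*

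If the effect of ineligible subjects is of interest, exclude them only in a labelled sensitivity analysis. The missing-data plan then applies to dropouts as it stands.

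The cost is one or two sentences of SAP text and no new data. If the sponsor already meant the pre-dose case, its intended handling of withdrawals does not change. The wording should be settled before unblinding for the final analysis, so that the choice of dataset cannot be influenced by the results.

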Study HU-9001 were modeled using the DiliSym™ proprietary software that is currently the focus of a collaboration between the U.S. Food and Drug Administration (FDA) and The Hamner Institutes for Health Sciences [17]. This analysis indicated that subjects given entolimod had a pattern of minor hepatocyte loss and recovery similar to that observed in healthy subjects receiving commercially available heparin drug products (e.g., heparin, dalteparin, enoxaparin, adomiparin). Other laboratory abnormalities associated with entolimod administration were asymptomatic hyperglycemia and transient hypophosphatemia. All of these laboratory abnormalities were perceived to be transient and self-limiting, have no serious clinical implications, and require no monitoring or intervention. Such effects were seen following administration of IL-6 in patients with cancer [18] and, thus, are likely secondary consequences of entolimod-mediated induction of this cytokine.

Transient decreases in blood pressure and increases in pulse rate observed in Studies HU-7014/HU-9001 were also likely the result of entolimod-mediated IL-6 induction [19]. Most of the changes in blood pressure were within the normal range and were imperceptible to subjects, although a minority of study participants did describe dizziness and orthostatic syncope occurred in 1 subject. For those subjects that developed blood pressures below the normal range, the time to return to normal averaged ~6 hours, indicating that hypotension following entolimod administration is typically not long lasting. No elevations of serum creatinine or blood urea nitrogen (BUN) consistent with renal hypoperfusion were evident in any subject. Observations of hypotension were managed at the investigator's discretion in both Studies HU-7014 and HU-9001. Consequently, such changes were addressed inconsistently, with neither the minimum absolute blood pressure nor the maximum decrease from baseline necessarily prompting an investigator decision to administer intravenous (IV) fluids. Only 13 of 150 subjects (8.7%) received IV fluids and only 1 subject (0.6%) was given IV dopamine; the rationale for administering a pressor agent to this subject was unclear since they only had transient asymptomatic Grade 2 hypotension and were discharged normotensive the following day.

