3.4 Primary Study Endpoints

Immunogenicity

- Changes of the anti- A/H1N1, anti-A/H3N2, and anti-B influenza virus strains serum circulating antibodies (as assessed using hemagglutination inhibition (HAI) assay) levels.

Safety

- All adverse events (AEs), including dose limiting toxicities (DLTs); laboratory abnormalities; oxygen saturation and vital sign changes, and adverse electrocardiogram (ECG) findings

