6.10 Examinations and Procedures

- Physical examinations will be limited to cardiac, pulmonary, abdominal, integumentary, and gross neurological evaluation, and to other systems based on specific subject complaints.
- Medical history is to be documented at Screening for each subject
- Vital signs, including pulse, orthostatic blood pressure, heart rate, respiratory rate, oxygen saturation and temperature will be measured.
- Height and weight will be obtained at the screening visit; weight will be obtained at each additional visit. Body mass index (BMI) will be recorded.
- A 12-lead electrocardiogram (ECG) will be performed. The Investigator will review and assess all abnormal results for clinical significance. Any post-baseline ECG abnormalities assessed as clinically significant will be recorded as AEs.
- Prior/Concomitant medications will be assessed at every site and remote visit.

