7.3 Subject Population(s) for Analysis

The primary analysis uses a modified intent-to-treat principle. Patients will be analyzed based on randomized arm using methods described previously. Exploratory analyses will assess whether a differential sex-based response to treatment exists for the primary outcomes and secondary outcomes of FI and QOL, using interaction terms in regression models.

8 Safety and Adverse Events

For safety analyses, AEs will be classified using the Medical Dictionary for Regulatory Activities (MedDRA). The severity of AEs will be graded by the investigator according to the Guidance for Industry Toxicity Grading Scale for Healthy Adult and Adolescent Volunteers Enrolled in Preventive Vaccine Clinical Trials. Concomitant medication use will be coded using the World Health Organization Drug Dictionary (WHODRUG) into Anatomical Therapeutic-Chemical classification (ATC) codes; these data descriptions will particularly focus on supportive medications and care provided in response to any study-study-induced adverse effects and to therapies for GVHD. For ECG assessment of QT intervals, correction by both the Bazett and Fridericia methods will be applied, and the data will be summarized by CTCAE grading categories in terms of absolute QTc and maximal QTc change from baseline.

A safety analysis will be conducted after 20 patients (5 per arm) have been randomized and completed the one-week safety follow-up period. After the last subject has completed their one-week safety follow-up period, there will be a temporary halt in additional participation pending analysis of safety outcomes, anticipated to be no longer than seven days. A safety report will be generated after the 20th patient completes 1 week follow up, summarizing all adverse events overall and by study arm while maintaining blind (groups denoted as A-D in random order). If appropriate, as described below, unblinded and subject-level adverse event data will be provided. Adverse events, both short term (14 days) and long term (through 365 days), will continue to be collected with ongoing monitoring as specified in the Data Safety Monitoring Plan (DSMP).

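### Vital sign changes are a primary safety endpoint, but section 7.2 specifies no within-subject change, worst value or threshold count for blood pressure, and no rule says when a vital-sign abnormality becomes an AE

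*Combined protocol and SAP*

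**What the plan says.** All references are to the combined protocol and SAP.

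- **Endpoint.** Section 3.4 lists, under primary safety endpoints, "laboratory abnormalities; oxygen saturation and vital sign changes, and adverse electrocardiogram (ECG) findings".
- **Measurement.** Section 6.2 and Table S-1 (footnotes d and q) call for vital signs with orthostatic pressures before dosing and at 2, 4 and 6 hours. Section 6.2 adds a reassessment before discharge.
- **Analysis.** Section 7.2 states "Data will be described and summarized by study drug assignment" and time point, then "Descriptive summaries will include sample size, mean and standard deviation, median, 25th and 75th percentiles, minimum and maximum for continuous variables", with percentages for categorical variables. Vital signs appear once, in a list: "laboratory abnormalities, vital signs/oxygen saturation, body weight, virology data, quality of life and frailty index status will be described and summarized".
- **QTc, for contrast.** The opening text of section 8 has QTc "summarized by CTCAE grading categories in terms of absolute QTc and maximal QTc change from baseline".
- **AE rules.** Section 6.10 says "Any post-baseline ECG abnormalities assessed as clinically significant will be recorded as AEs". Section 6.11 has a matching rule for laboratory values, and section 8.1 adds another. There is none for vital signs.
- **History.** Section 1.4.2.1 reports that "Most of the changes in blood pressure were within the normal range and were imperceptible to subjects", that recovery of below-normal pressures took about 6 hours on average, and that investigators handled hypotension inconsistently. Section 1.4.2.2 and the colorectal cancer study report the same transient, generally symptomless pattern. Section 1.6 lists blood pressure decreases second among six potential risks.

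**The concern.** The endpoint is a change within a subject. The specified analysis describes an arm at a time point. Falls in a minority of subjects, possibly at different readings, are diluted in a mean or median. A fall can also be large relative to the subject's own baseline without giving a low absolute value.

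The usual backstop is the AE table. Here a symptomless fall reaches it only if an investigator decides that it is an AE, and the earlier studies show that such decisions varied. The same matters for oversight: section 3 names AE data as what the DSMB receives for dose escalation, and the unblinding trigger in section 8.4 counts AEs.

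At stake is how well the trial can describe a known drug effect in people aged 65 or over, by dose, when section 7.2 says that it is meant to assess safety and identify a dose for phase III. The primary immunogenicity analysis is not affected.

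**Working it through.** The plan states no figure on this point, so there is none to reproduce. The check has two parts.

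**1. What is specified, side by side**

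| Item | QTc | Laboratory values | Blood pressure, heart rate |
|---|---|---|---|
| Maximal change per subject | Yes (section 8) | No | No |
| Graded categories in the analysis | Yes (section 8) | Not spelled out; abnormalities are summarised (7.2) | No |
| Rule for becoming an AE | Yes (6.10) | Yes (6.11, 8.1) | No |

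Hypotension limits do exist, under Support for Hypotension, but they serve supportive care and are not carried into section 7.2.

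**2. An illustration of the consequence**

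From the documents: 25 per arm (7.1); three timed post-dose readings (Table S-1); systolic pressure of at least 110 mmHg at screening and an upper limit near 160 mmHg (4.2).

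Assumed, because the documents give no variance or rate: systolic pressure with mean 132 and between-subject SD 12 mmHg, clipped to 110–159; reading SD 7 mmHg; a fraction f of the active arm falls 30 mmHg at m of the three readings; placebo f = 0.

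*Mean.* Shift per time point = f × 30 × m/3.

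| f | m = 1 | m = 2 | m = 3 |
|---|---|---|---|
| 0.087 | 0.9 | 1.7 | 2.6 |
| 0.20 | 2.0 | 4.0 | 6.0 |
| 0.30 | 3.0 | 6.0 | 9.0 |

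Without falls, the SD of the difference between two arm means is about √[2 × (12² + 7²)/25] = 3.9 mmHg. Simulation with f = 0.20 and m = 1 gives about 4.1. A 2 mmHg shift is inside that noise; 6 mmHg is about 1.5 times the no-fall SD.

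*Per-subject count, fall above 20 mmHg (an illustrative cut, not a proposed limit).*

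- The difference of two readings has SD 7 × √2 = 9.9 mmHg.
- Placebo: one reading exceeds 20 by chance with probability 1 − Φ(20/9.9) ≈ 2.2%. The largest of three lies between 2.2% and 6.5%; simulation gives 5–6%.
- A subject with one affected reading exceeds 20 with probability of about Φ(10/9.9) ≈ 0.84, or about 0.85 counting the other two readings. For f = 0.20: 0.20 × 0.85 + 0.80 × 0.055 ≈ 21%.
- With all three readings affected, the simulated share is about 24%.
- With one reading affected, the share is 12% at f = 0.087 and 29% at f = 0.30.

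*Sensitivity to reading noise.* A second set-up (mean 135, between-subject SD 12–18, 5 of 25 subjects falling at one reading) gives counts above 20 mmHg rising from 0.6 to 4.9 of 25 with reading SD 6, and from 2.3 to 5.9 with reading SD 8.

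*Planned minimum.* In the first set-up with f = 0.20 and m = 1, some reading is below 90 mmHg in about 62–64% of active arms and 1% of placebo arms. In the second set-up it is 50–71% of active arms, yet only 13–21% of the subjects who fell reached below 90.

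**The case against.** There is a good deal to say for the plan.

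- **Change is not excluded.** Section 7.2 never limits vital signs to levels, and section 3.4 says changes. A sensible analyst might tabulate change anyway. That stands; the defect is that it is left unspecified.
- **The minimum carries a signal.** A reader might infer that the trial could report no blood pressure effect while several subjects had large falls. The documents do not support that as a likely outcome: the minimum is an individual reading and, in the illustration, often drops below 90 on active drug. What it cannot give is a count or the size of a fall.
- **Other routes exist.** AEs and supportive care are summarised, AEs are sought at every contact and by examination where appropriate, the AE definition does not require symptoms, and the DSMB sees unblinded data. So it would be wrong to infer that falls must go unreported.
- **Falls may last.** Recovery of about 6 hours suggests that many falls would span several readings, which moves the mean by 4–6 mmHg rather than 2. The range above allows for this.
- **Rates and doses.** The 8.7% is an earlier rate of IV-fluid use, not of 30 mmHg falls; 20% and 30% have no source in the documents. By the counts in section 1.4.2.1, 132 of those 150 subjects received at least 24 µg, whereas this trial gives 1–10 µg. The true rate may be much lower.
- **Rank of the risk.** A reader might take hypotension as the leading known harm. Sections 1.4.2.1, 1.4.2.2 and 1.6 put flu-like symptoms first.

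**Conclusion.** The concern holds in a limited form. A primary safety endpoint defined as change has no specified change analysis for vital signs, no worst value per subject and no threshold count, and a vital-sign abnormality has no stated route into the AE tables. The planned summaries would reveal some falls, but not the number of subjects affected or the depth from their own baseline.

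The size is illustrative only and rests on assumed variances and rates: with 20% of an arm falling 30 mmHg, a mean shift of 2–6 mmHg per time point against shares of about 21–24% and 5–6%. Even the better table will not be decisive at this sample size. Five of 25 has an exact 95% interval of about 7% to 41%, and one of 25 about 0% to 20%. The gain is complete description by dose, not a powered test.

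**What to change.** Add to section 7.2, by arm:

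1. change from the Day 0 pre-dose value at each post-dose reading;
2. each subject's maximum fall in systolic and diastolic pressure, including orthostatic measurements, and maximum rise in heart rate over the 2, 4 and 6 hour and pre-discharge readings, shown as distributions;
3. the number and proportion of subjects in pre-specified categories, with exact confidence intervals, counted whether or not recorded as AEs.

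State also how a vital-sign abnormality comes to be recorded as an AE, as sections 6.10 and 6.11 do for ECG and laboratory findings.

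The sponsor should set the categories after reconciling the blood pressure definitions. The orthostatic criterion in section 4.2 uses a systolic and a diastolic fall. The Support for Hypotension text gives two different fall limits, both for systolic pressure, and ties falls to symptoms or orthostatic measurement. As that text can be read to leave out a symptomless resting fall, the distributions in item 2 are needed as well as the counts. A dose-ordered comparison is optional.

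The cost is SAP wording and one more descriptive table, with no new visit or procedure. Some placebo subjects will cross a limit by chance (5–6% in the illustration), so the counts must be read against placebo.
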